## Patient recruitment

After the study opens, we anticipate that we will recruit 8-10 patients per month and we will require a maximum of 16 months for recruitment and a further 12 months for follow up. We anticipate that we will be able to report our data in abstract form within 2.5 years of opening the study and have a manuscript in press within 3 years.

## 11 Statistics and powering of this study

**Design** The null hypothesis is that the treatment in the nurses arm is not more efficacious than treatment by the GP

- Study: randomised controlled trial
- Parallel design
- Interventions: 2
- Outcome: IBS severity scoring system, 0-500 (Francis et al., 1997), Mild 75-175, Moderate 175-300, Severe >300
- Expected loss to follow-up: 10%
- Lost due to GP deviation from protocols: 15%
- Alpha: 0.05, 2 sided sd = 84.9000

## **Stratification**

- 1. By gender (male v female)
- 2. They will be stratified by their baseline IBS SSS score into 2 groups: (a) mild or moderate (b) severe to ensure the arms are balanced for severity of symptoms.

## Sample size

We assume 75% of participants will fall into the mild to moderate group (a) and 25% into the severe group (b). We anticipate that there will be a different effect size in each group so we will test them separately. A reduction in score of 50 is the minimum clinically important difference we aim to achieve. However, we also know that 50% of the control group will improve with NICE suggested treatments

The expected value of the primary outcome for the trial in the control group is 125.4 in the mild to moderate group, and 372 in the severe group. The standard deviation is 53.4 and 66.0 in the mild to moderate group and severe groups respectively. We have assumed that 5% of the control patients will be treated in a more similar way to the intervention group, leading to an inflation of the control group change in outcome measure. This makes a change in the difference between control and intervention of 47.5 that we wish to detect. Using a power of 85%, and alpha of 5% gives 72 in total from the severe group and 48 in the mild to moderate group. Each group is randomised half to intervention and half to control. After allowing for loss to follow-up of 10%, the severe group rises to 80 and the mild to moderate group to 54. Giving a total needed of 134 participants.

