**Research plan:**, After providing informed consent to participate, eligible patients will be stratified by IBS severity and gender, then randomised to care by a GP following NICE guidance or to a research nurse, specially trained to use structured investigations to identify organic pathology and equipped with treatment protocols targeting abnormal investigation results.

Recruitment of 134 patients will give the study 85% power to detect clinically significant improvement in the primary endpoint, IBS severity scoring system (IBSSSS) score at one year allowing for 10% patients loss to follow up and 5% GP deviation from NICE guidance.

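### The total of 134 needs 80 severe patients (60%), but the same paragraph assumes 25% severe; on that mix the separate severe-group test has about 48% power, not 85%

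*Protocol*

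**What the plan says.** All the inputs stand in section 11 of the protocol, mostly in the Sample size paragraph.

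- Expected mix: "We assume 75% of participants will fall into the mild to moderate group (a) and 25% into the severe group (b".
- Plan for testing: "We anticipate that there will be a different effect size in each group so we will test them separately".
- Target difference: "This makes a change in the difference between control and intervention of 47.5 that we wish to detect".
- Spread: "The standard deviation is 53.4 and 66.0 in the mild to moderate group and severe groups respectively".
- Evaluable numbers: "Using a power of 85%, and alpha of 5% gives 72 in total from the severe group and 48 in the mild to moderate group".
- After 10% loss to follow-up: "the severe group rises to 80 and the mild to moderate group to 54", which sum to 134.

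Section 9, the demographics part of section 10 and the Stratification paragraph of section 11 use severity only as a randomisation stratum, to balance the arms. The eligibility criteria and the recruitment text set no minimum, cap or enrichment by severity. On timing, section 10 says "we will recruit 8-10 patients per month and we will require a maximum of 16 months for recruitment". The Summary says "Recruitment of 134 patients will give the study 85% power to detect clinically significant improvement in the primary endpoint".

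Two further paragraphs of section 11 bear on this. Analysis describes one model of the severity score, adjusted for its baseline value, that yields one average effect of treatment. Subgroup Analyses disclaims power for subgroup differences and makes their interpretation depend on the overall result.

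**The concern.** The 75/25 mix is stated and then never used. Each severity group is sized for its own 85% test, and the two totals are added as though recruitment would deliver 60% severe and 40% mild to moderate. Stratified randomisation balances the arms within each severity group; it does not change how many severe patients arrive. The assumed mix and the required split cannot both hold for the same 134 patients.

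At stake is the stated justification for the sample size. If the mix is right, one of the two tests from which 134 is built has roughly an even chance of detecting the target difference, while the other has far more patients than it needs. The protocol is also unclear about what its primary test is: two separate tests in one paragraph, one average effect in the next.

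**Working it through.** **Inputs** (section 11): difference 47.5; SD 66.0 (severe) and 53.4 (mild to moderate); two-sided alpha 0.05; power 85%; 1:1 allocation within each group; 10% loss; mix 75/25.

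**1. Reproducing the plan's figures.** Two-sample t-test with standardised difference d = 47.5/SD.

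| Group | d | n per arm, solved | n per arm, rounded up | Evaluable total | ÷ 0.90 |
|---|---|---|---|---|---|
| Severe | 47.5/66.0 = 0.720 | 35.7 | 36 | 72 | 80 |
| Mild to moderate | 47.5/53.4 = 0.890 | 23.7 | 24 | 48 | 53.3, so 54 |

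The sum is 80 + 54 = 134, so every stated figure reproduces. The normal approximation gives 70 and 46, so the protocol evidently used the t-test. The fault lies in combining the groups, not in sizing them.

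**2. Implied mix against assumed mix.** 80/134 = 59.7% severe is required; 25% is assumed.

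**3. Power at the assumed mix, same t-test.**

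- Severe: 134 × 0.25 = 33.5 recruited; × 0.90 = 30.2 evaluable; 15 per arm; power 47.7%.
- Mild to moderate: 134 × 0.75 = 100.5 recruited; × 0.90 = 90.5 evaluable; 45 per arm; power 98.7%.

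**4. Sensitivity of the severe-group figure.**

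- Normal approximation instead of the t-test: about 50–51%.
- No loss to follow-up at all (about 17 per arm): about 53%.
- Severe share of 30%, 40% or 50% instead of 25%: about 56%, 69% or 78%. Power reaches 85% only at about 60%.
- Baseline adjustment: the residual SD is 66.0 × √(1 − r²). The protocol gives no r, so values are assumed. For r = 0.3, 0.5 and 0.7 the SD is 63.0, 57.2 and 47.1, and power with 15 per arm is about 51%, 59% and 76%.

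**5. What 80 severe patients would take.** 80/0.25 = 320 recruits. At 8–10 per month that is 32–40 months. The stated maximum of 16 months yields 128–160.

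**6. The pooled comparison at 134.** 134 × 0.90 = 120.6, so about 60 evaluable per arm.

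- With the SD of 84.9 listed in the Design list of section 11: power about 86%.
- With the within-stratum SD, √(0.75 × 53.4² + 0.25 × 66.0²) = 56.8: power over 99%.

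The protocol does not say where 84.9 comes from, and the choice of SD matters. The stated control values of 125.4 and 372 differ by 246.6. A crude comparison that ignored severity would therefore carry an SD of about √(56.8² + 0.25 × 0.75 × 246.6²) = 121, with power of about 57%. The planned baseline adjustment is meant to remove most of that between-group spread, so the power statement should refer to the adjusted comparison.

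**The case against.** The strongest reply is that separate testing appears only in the sample size paragraph. The Analysis paragraph plans one baseline-adjusted average effect, and the Subgroup Analyses paragraph disclaims power for subgroups and calls for cautious reading. On that plan the severe-group test is not the primary analysis, and about 60 evaluable patients per arm give about 86% power with the listed SD of 84.9. This stands as far as the trial as a whole is concerned. It does not remove the contradiction, because 134 is derived solely from two separate 85% tests; the two later paragraphs add to the inconsistency.

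Four stronger readings are tempting, and the protocol does not support them.

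- A reader might infer that the Summary falsely claims 85% power in the severe group. It does not: its 85% is for the study as a whole, and a pooled comparison can reach that level. Only the derivation behind the figure is unsound.
- A reader might expect a null severe-group result to be taken as an adequately powered negative. The caution in Subgroup Analyses weakens that fear.
- A reader might multiply the two powers to get a chance of success in both groups. No rule in the protocol requires both tests to succeed.
- A reader might conclude that 134 cannot be recruited in 16 months. It lies within the 128–160 that the stated rate yields; only the lowest rate falls short, by 6.

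It is also fair to say that 48% is an unadjusted figure while the planned model adjusts for baseline. It is the like-for-like comparison with the protocol's 85%, and adjustment at the assumed correlations still leaves power below 85%.

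**Conclusion.** The sample size paragraph contradicts itself. It assumes 25% severe and needs 60%, with no means stated of obtaining the difference. Under its own mix, difference, SDs and loss rate, the separate severe-group test has about 48% power (about 51–76% with assumed baseline correlations of 0.3–0.7) against the 85% claimed, and the mild to moderate test has about 99%. The conclusion rests on the 75/25 assumption and the absence of a quota; it does not depend on which power formula is used. It is a defect in the justification of the sample size and in the status of the separate tests. It is not evidence that the overall comparison at 134 is underpowered.

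**What to change.** Keep 134 and amend the protocol text.

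1. In the Sample size paragraph, state the split expected under 75/25 (about 34 severe and 100 mild to moderate recruited; about 30 and 90 evaluable) and the unadjusted power of each group for 47.5 points (about 48% and 99%). Withdraw the 85% claim for the severe group.
2. Replace the plan for separate tests with the pooled baseline-adjusted comparison of the Analysis paragraph as the single primary test. Label severity-specific results exploratory, in line with Subgroup Analyses.
3. Rest the 85% statement, here and in the Summary, on that pooled comparison. State the SD used and its source: about 86% with 84.9 and 60 per arm, higher with the within-stratum SDs.

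The cost is no extra patients, but it is more than an editorial change: the basis of the sample size moves from two tests to one, and the severe-group result loses its claim to adequate power. If the sponsor wants a confirmatory severe-group test, the alternatives are a justified 60/40 recruitment quota or a total of about 320. At 25% severe, either means finding about 320 eligible patients to obtain 80 severe ones, which the stated recruitment period does not allow.

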## Stratification

## **Analysis**

Means ± SD values or percentiles appropriate to the distribution will be reported for the primary outcome and secondary outcomes by treatment group. A statistical model will be fitted with IBS severity scoring system[23] as the dependent variable. This will be adjusted for baseline assessment of the IBS severity score. A random effects model will be explored. A point estimate, 95% confidence interval and p-value will be reported for the average treatment effect. Residual values will be examined for an approximate normal distribution. If values are highly skewed then a transformation or robust statistical methods will be used instead.

Mixed linear regression models will be used to compare continuous outcomes between treatment groups by adjusting for corresponding metric calculated at baseline and random site effect.

For assessing group difference in demographic covariates, including age, sex and socioeconomic status, linear regression models will be used to compare continuous and ordinal variables, logistic regression will be used to compare categorical variables, and Poisson regression models will be used to compare event rates, while adjusting for a random site effect. For analysis of adverse events, formal statistical comparisons will only be performed when there are enough observed events. If outliers exist, a robust Poisson regression model will be used instead.

Missing data for secondary outcomes will not be imputed. Available case analysis method will be used for secondary analyses.

Two sided p-value will be reported and a 5% significance level will be used to declare statistical significance. For all above mentioned secondary analyses, the false discovery rate will be controlled using the adaptive Benjamini-Hochberg procedure.

A detailed statistical analysis plan will be drafted and approved by the Trial Management Group before data lock.

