## **Subgroup Analyses**

The study is not powered to detect subgroup differences. Interpretation of any subgroup analyses will depend on whether the overall analysis demonstrates a significant treatment group difference. If performed the subgroup analyses will be conducted for the primary outcome and will be interpreted with caution.

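### The trial is sized for two separate severity-group tests, but the primary analysis is one pooled model, so the stated 85% power is not the power of the analysis described

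*Protocol*

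**What the plan says.** Section 7 of the Protocol gives the primary endpoint as improvement in IBSSSS at one year and does not say which test decides it.

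Four places in the Protocol bear on that test:

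- **Section 11, Sample size.** On the two severity groups: "We anticipate that there will be a different effect size in each group so we will test them separately". The target is common to both: "This makes a change in the difference between control and intervention of 47.5 that we wish to detect". Then: "Using a power of 85%, and alpha of 5% gives 72 in total from the severe group", with 48 for the mild to moderate group. After 10% attrition these become 80 and 54, total 134.
- **Section 11, Analysis.** One model for the IBS severity score, adjusted for its baseline value: "A point estimate, 95% confidence interval and p-value will be reported for the average treatment effect". No severity-specific test appears. The false discovery rate control is for secondary analyses only.
- **Section 11, Subgroup Analyses.** "The study is not powered to detect subgroup differences", and "Interpretation of any subgroup analyses will depend on whether the overall analysis demonstrates a significant treatment group difference".
- **Section 1, Summary.** "Recruitment of 134 patients will give the study 85% power to detect clinically significant improvement in the primary endpoint".

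The design list that opens section 11 also carries "Alpha: 0.05, 2 sided sd = 84.9000". The Sample size paragraph does not use that standard deviation.

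**The concern.** The sample size and the analysis answer different questions. The 134 is the sum of two stand-alone comparisons, while the Analysis paragraph makes a single comparison across both groups. A reader of the Summary would take 85% as the power of that single comparison.

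What counts as success is therefore open. If the two severity-group tests are primary, the Protocol does not say whether one or both must be significant, and it does not divide the 5%. If the pooled model is primary, the power statement was calculated for something else, and the sentence on separate testing has no place in the plan. The choice affects both the error rate and the power that the trial can claim.

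**Working it through.** **Inputs, all from section 11.** Difference 47.5 in both groups; SD 66.0 (severe) and 53.4 (mild/moderate); two-sided 5%; power 85%; 1:1 allocation; 10% attrition; design-list SD 84.9.

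**1. The plan's own figure.** A two-sample t-test calculation needs 35.66 per arm, rounded up to 36, for severe (72 in total), and 23.70 per arm, rounded up to 24, for mild/moderate (48 in total). Attrition: 72/0.9 = 80 and 48/0.9 = 53.3, rounded up to 54; total 134. The figures are reproduced. One-sided calculations give 58 and 38 and do not fit, so each group was sized for its own two-sided 5% test.

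**2. Power of each test at those sizes.** Severe, 36 per arm: 0.853. Mild/moderate, 24 per arm: 0.855. So 85% is right for each test taken alone.

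**3. If the two separate tests are primary.**

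| Success rule | Familywise error, both nulls true | Power at 47.5 in both groups |
|---|---|---|
| Either suffices, 5% each | 1 − 0.95² = 9.75% | 1 − 0.147 × 0.145 = 97.9% |
| Both required, 5% each | no inflation | 0.853 × 0.855 = 73% |
| Either suffices, 2.5% each | at most 5% | about 77.5% per group |

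Keeping 85% per group at 2.5% each would need 86 + 58 evaluable, that is 96 + 65 = 161 randomised.

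**4. If the pooled model is primary.** Assume a common difference of 47.5, 60 evaluable per arm, and the within-group SD standing in for the residual SD after baseline adjustment.

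- Mix of 72/48: SD = √(0.6 × 66.0² + 0.4 × 53.4²) = 61.3; power 98.8%.
- Mix of 25% severe, 75% mild/moderate: SD = √(0.25 × 66.0² + 0.75 × 53.4²) = 56.8; power 99.5%.
- Difference detectable at 85% power: about 31 points (SD 56.8) to 34 points (SD 61.3).

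**5. The SD of 84.9.** Used in a pooled test with 60 per arm, it gives 86% power; 85% would need 118 evaluable, or 132 randomised. But √(66.0² + 53.4²) = √(4356 + 2851.56) = 84.9. Because the required N is proportional to SD², an SD built this way returns roughly the sum of the two group sizes by algebra. It is not the within-group SD (about 57 to 61). Nor is it the total SD implied by control means of 125.4 and 372: with variance within + p(1 − p) × 246.6², that is about 135 at 60% severe and 121 at 25% severe.

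**The case against.** **The 85% is correct for something.** True. It is the power of each severity-group test at the 80/54 split. A reader might infer that 85% is wrong under every reading; steps 1 and 2 show otherwise. The fault is that the figure is carried over to a different analysis.

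**The design-list SD gives about 86% for a pooled test.** Also true, and the sponsor may say so. But the Protocol does not link 84.9 to the pooled model, and step 5 shows that the agreement with 134 follows from how the number is built.

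**The Subgroup Analyses paragraph.** A reader might infer that "The study is not powered to detect subgroup differences" contradicts sizing each group at 85%. It most naturally refers to a difference in effect between groups, that is an interaction, and then it is true. The standard error of that difference is √(4 × 66.0²/72 + 4 × 53.4²/48) = 21.9, so 85% power needs about 3.0 × 21.9 = 66 points, above the 50-point minimum important difference. The gate on the overall result is a conservative convention.

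**Error inflation is not established.** This stands as a limit on the point. If the stratum tests are subgroup analyses read only after a significant overall result, error under the global null stays at 5%. The 9.75% applies only if two stand-alone tests are primary and either one suffices, which the Protocol never states.

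**The analysis plan may settle it.** It can add detail such as an alpha allocation. It does not remove the conflict between two paragraphs of the Protocol and the Summary.

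**Conclusion.** The point holds as an inconsistency inside the Protocol. The sample size rests on two separate two-sided 5% tests, the analysis is a single pooled test, and the Summary's 85% belongs to the former.

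Its size depends on which is meant. With two primary tests, power is about 73% if both must succeed, or familywise error is 9.75% if either suffices at 5%. With the pooled model, power is about 99% for 47.5 points. That last figure assumes the same effect in both groups, although the Protocol expects different effects, and a residual SD of about 57 to 61; with the unexplained 84.9 it would be about 86%.

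A reader might infer that the trial is underpowered. For the pooled, baseline-adjusted test, these inputs do not support that. All stratum figures are for the planned 80/54 split; whether recruitment would deliver that split, given the Protocol's expectation of 75% mild to moderate, is a separate question.

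**What to change.** 1. Name one primary test, and make the Summary, Sample size and Analysis paragraphs agree on it. The pooled baseline-adjusted effect on one-year IBSSSS at two-sided 5% fits the Analysis and Subgroup Analyses paragraphs as they stand.
2. If that test is chosen, delete the clause on separate testing and report the stratum estimates with confidence intervals as secondary.
3. Explain or remove the SD of 84.9 before any new power figure is written.
4. Restate the power for the named test with its assumptions. For the pooled test: 120 evaluable, common 47.5-point difference, within-group SD of about 57 to 61, power about 99%, or 85% for about 31 to 34 points.
5. If two primary tests are kept, state whether one or both must succeed, control alpha if either suffices, and restate the power.

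The gate in the Subgroup Analyses paragraph need not change; replacing it with an interaction test would be a preference.

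Cost: wording in the Protocol and analysis plan, with no new data. Under the pooled choice, stratum results become secondary. Under two tests at 2.5% each, either power falls to about 77.5% per group or the total rises to 161.

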## Stratification

## **Analysis**

Means ± SD values or percentiles appropriate to the distribution will be reported for the primary outcome and secondary outcomes by treatment group. A statistical model will be fitted with IBS severity scoring system[23] as the dependent variable. This will be adjusted for baseline assessment of the IBS severity score. A random effects model will be explored. A point estimate, 95% confidence interval and p-value will be reported for the average treatment effect. Residual values will be examined for an approximate normal distribution. If values are highly skewed then a transformation or robust statistical methods will be used instead.

Mixed linear regression models will be used to compare continuous outcomes between treatment groups by adjusting for corresponding metric calculated at baseline and random site effect.

For assessing group difference in demographic covariates, including age, sex and socioeconomic status, linear regression models will be used to compare continuous and ordinal variables, logistic regression will be used to compare categorical variables, and Poisson regression models will be used to compare event rates, while adjusting for a random site effect. For analysis of adverse events, formal statistical comparisons will only be performed when there are enough observed events. If outliers exist, a robust Poisson regression model will be used instead.

Missing data for secondary outcomes will not be imputed. Available case analysis method will be used for secondary analyses.

Two sided p-value will be reported and a 5% significance level will be used to declare statistical significance. For all above mentioned secondary analyses, the false discovery rate will be controlled using the adaptive Benjamini-Hochberg procedure.

A detailed statistical analysis plan will be drafted and approved by the Trial Management Group before data lock.

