#### 9. Randomisation

Once eligible patients have signed the structured consent form, they will be randomised 1:1 to either usual following NICE guidance by the GP or a checklist of structured investigations

and management. The Hull Health Trials Unit (HHTU) will provide and maintain a purpose built, web-based data capture system with integrated randomisation. Following assessment of baseline outcomes, participants will be randomised 1:1, IBSSSS score (mild + moderate v severe) and patient gender (male v female). It is not possible to blind nurses or participants to the intervention but researchers analyzing data will be blind to treatment allocation. Access to the randomisation system is managed by HHTU staff and users are granted role-based access restricted to sites they are working at.

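### Gender is a randomisation stratum but is in neither stated adjustment set, while sex is instead to be compared between arms at baseline

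*Protocol*

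**What the plan says.** Section 9 (Randomisation) sets the strata: "participants will be randomised 1:1, IBSSSS score (mild + moderate v severe) and patient gender (male v female"). The demographics part of Section 10 and the Stratification list in Section 11 repeat both factors.

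The Analysis text in Section 11 then states:

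- Primary model, with the IBS severity score as dependent variable: "This will be adjusted for baseline assessment of the IBS severity score". On clustering: "A random effects model will be explored".
- Continuous outcomes: mixed linear models comparing the arms "by adjusting for corresponding metric calculated at baseline and random site effect".
- Baseline characteristics: "For assessing group difference in demographic covariates, including age, sex and socioeconomic status, linear regression models will be used". The sentence goes on to logistic models for categorical variables and Poisson models for event rates, all with a random site effect.
- Multiplicity: "For all above mentioned secondary analyses, the false discovery rate will be controlled using the adaptive Benjamini-Hochberg procedure".
- Further detail: "A detailed statistical analysis plan will be drafted and approved by the Trial Management Group before data lock".

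**The concern.** A factor used to stratify randomisation is normally carried into the analysis model. Stratification makes the arms alike on that factor, so chance imbalance in it no longer adds to the sampling variation of the treatment estimate. A model without the factor still counts its variance as residual noise. The reported standard error is then larger than the true one, the confidence interval is wider than the design earns, and the test rejects less often than its nominal 5%. The baseline score largely covers the severity stratum, so gender is the stratum left out.

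The plan does give sex a role, but in a comparison between arms. Any baseline difference between randomised arms is due to chance, and stratification also limits the difference in gender. Such a test answers no question about the treatment.

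The scope of the false discovery rate control is a smaller matter. The demographic comparisons stand above the sentence that applies it, and nothing says whether they are in or out. If they were in, tests known to be null would make it harder to declare the real secondary outcomes.

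**Working it through.** **1. The plan's own figure.** Inputs from Section 11 (Sample size): difference 47.5, SD 66.0 (severe) and 53.4 (mild to moderate), two-sided 5%, power 85%, 1:1 allocation. A two-sample t-test calculation gives 35.66, so 36 per arm and 72 in total (severe), and 23.70, so 24 per arm and 48 in total (mild to moderate). With 10% loss: 72/0.9 = 80 and 48/0.9 = 53.3, so 54; the total is 134. This matches the protocol. The calculation uses no covariates, so this point does not touch it.

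**2. Cost of leaving gender out, closed form.** Let R² be the share of the primary model's residual variance that gender explains. The protocol gives no value, so 5% and 10% are assumptions. With gender balanced between arms:

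- Ratio of reported to true standard error = 1/√(1 − R²)
- Type I error = 2 × [1 − Φ(1.96/√(1 − R²))]

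| R² | SE ratio | Type I error |
|---|---|---|
| 0 | 1.000 | 5.0% |
| 5% | 1.026 | 4.4% |
| 10% | 1.054 | 3.9% |

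On the variance scale the reported interval is as wide as if 5% or 10% of the 72 + 48 = 120 evaluable participants were missing: 120 × 0.05 = 6, or 120 × 0.10 = 12.

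**3. What R² means in points.** Assume 70% women and a residual SD of 60 (neither is in the protocol). A gender difference g, after baseline adjustment, gives R² = 0.21g²/(0.21g² + 3600), where 0.21 = 0.7 × 0.3. So R² = 5% needs g of about 30 points and R² = 10% about 44. The minimum important difference in Section 11 is 50.

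**4. Simulation check.** Same assumptions, 120 evaluable, exact balance within gender, true difference 33 for power (also an assumption), 4,000 trials per scenario:

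| Gender effect (points) | Type I error without / with gender | Power without / with gender | Mean SE without / with gender |
|---|---|---|---|
| 0 | 5.0% / 4.8% | 85% / 85% | 11.0 / 11.0 |
| 20 | 5.1% / 5.2% | 83% / 84% | 11.1 / 11.0 |
| 40 | 3.9% / 4.6% | 82% / 85% | 11.5 / 11.0 |
| 60 | 3.3% / 5.0% | 80% / 85% | 12.1 / 11.0 |

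This agrees with the closed form. There is no measurable loss at 0 points and little at 20. Including gender costs nothing visible when it is not prognostic.

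**5. False discovery rate family, if the demographic comparisons were in it.** Assumptions: 8 independent secondary tests, 3 with a true effect (z shift 2.8), a two-stage adaptive Benjamini-Hochberg procedure at 5%, 2,000 runs. Average power for the true effects:

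| Null tests added | Power |
|---|---|
| 0 | 66% |
| 3 | 59% |
| 6 | 57% |
| 10 | 52% |

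These figures apply only under that reading of the text.

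**The case against.** **The primary outcome may hardly depend on gender.** Section 4 (Background) says that women report more symptoms and lower quality of life, but the same sentence on symptoms says that IBS severity is similar in the two sexes. The primary outcome is a severity score, and the model already adjusts for its baseline. A residual effect of 30 to 44 points would approach the minimum important difference. This stands. A reader might infer that the primary test is conservative as a matter of fact; the documents do not support that, because the loss depends on an R² that they do not give and may be nil. The closed form also assumes that gender stays balanced among those analysed, and 10% loss to follow-up is expected.

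**The false discovery rate family may already be right.** A reader might infer that the plan counts the demographic comparisons among the tests under control. The text never calls them secondary analyses, and the paragraph just before speaks of secondary outcomes and secondary analyses together. The natural reading leaves them out. What remains is an ambiguity.

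**The statistical analysis plan can settle this.** It can, and the protocol does not say that baseline score is the only covariate. A full covariate list is commonly left to that plan. But the protocol does name adjustment sets, a stratum is missing from both, and it positively plans the demographic comparisons. The promise of a later plan does not correct those statements.

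**A single pooled model may not be the primary analysis.** The Sample size text says that the severity groups will be tested separately, while the Analysis text refers to an average treatment effect. That conflict is separate. Gender is a stratum under either approach.

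**Conclusion.** The point holds as a matter of efficiency and clarity. Gender is a stratum and is named in neither adjustment set. There is no bias in the treatment effect, no inflated type I error and no effect on the sample size of 134.

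The cost ranges from nil, if gender is not prognostic for the one-year score, to a standard error about 3-5% too large and a type I error of about 4.4-3.9%, if gender explains 5-10% of residual variance. That range is an assumption, and the Background gives reason to expect the low end for the severity score. Quality of life, a secondary endpoint that the Background says is lower in women, may depend more on gender, although baseline adjustment will absorb part of that too.

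The between-arm comparisons of age, sex and socioeconomic status are uninformative after randomisation, above all for a stratified factor. Whether they enter the false discovery rate family is unclear. Only if they did would power for the secondary outcomes fall, in the illustration from about 66% to 59% with three added tests.

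**What to change.** 1. Primary analysis: include gender as a fixed covariate alongside continuous baseline IBSSSS. Word this so that it holds whether the analysis is pooled or within severity group, and reconcile that conflict with the Sample size text separately.
2. Secondary outcome models: add gender to the stated baseline value and random site effect.
3. Replace the between-arm demographic comparisons with a baseline table that describes each arm without p-values.
4. State that the false discovery rate family contains the secondary outcome analyses only.

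The cost is wording in the protocol or in the statistical analysis plan, before data lock. Gender is already recorded for every participant and held in the randomisation system. No new data are needed, and N = 134 stands.
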